### **3.0                   Introduction**

This statistical analysis plan (SAP) describes the statistical analysis to be completed by the AbbVie Clinical Statistics Department for study Protocol M16-009 Amendment 6 dated 30 January 2018.

This SAP will provide details to further elaborate statistical methods as outlined in the Protocol M16-009 and will describe analysis conventions to guide the statistical programming work. The SAP will be signed off before the study database is locked.

Analyses will be performed using SAS® version 9.4 (SAS Institute, Inc., Cary, NC 27513) or higher using the UNIX operating system.

### **4.0                   Study Objectives, Design and Procedures**

#### **4.1                   Primary Study Objective**

The primary objective of this study is to investigate long-term safety and efficacy of risankizumab during open-label treatment in patients with moderate to severe chronic plaque psoriasis.

#### **4.2                   Design Diagram**

This open label extension trial (OLE), investigates the additional safety and efficacy of the 90 mg dose of risankizumab. Approximately 100 patients who meet the entry criteria are planned for inclusion in this trial, rolling over from the preceding Study 1311.2 trial. The treatment will be open label.

[figure not shown]
The treatment period will be approximately four years of administration starting with first administration of risankizumab in either Trial 1311.2 or this study, followed by a 12 week follow up period. After 01-May-2018 and approval of the protocol Amendment 6 in each respective country, the next study visit will be the Extended EOS visit and therewith the last visit in this study. Patients who have completed the study without early treatment discontinuation will be offered to roll over to Study M15-997

open label extension (OLE) trial if they fulfill the inclusion and exclusion criteria for the Study M15-997 trial.

Patients rolling over from the preceding Trial 1311.2 will have to complete the treatment period in that trial, or complete the entire trial including the follow up period, reaching end of study. If, during the follow up period of the preceding trial (at any visit from Week 24 and onwards in Trial 1311.2) loss of response is detected, the patient can roll over in this extension trial. For this, loss of response is defined as  $< \text{PASI } 50$ .

Extended Visit 1 of this trial should preferably be performed as a combined visit the same day as End of Study visit of Study 1311.2, or within an interim period of maximum 6 weeks thereafter.

**Figure 1. Guideline for roll over of patients from Study 1311.2 to this study**

[figure not shown]

After the approval of protocol Amendment 6 in each respective country, all patients will follow Flow Chart (Extended Dosing Period) in the protocol and receive 90 mg risankizumab subcutaneously at their Extended Visit 1 (EV1). From EV1 onwards, risankizumab will be administered subcutaneously every 12 weeks during the trial. At EV2, if there is a lack of response, defined as  $< \text{PASI } 90$ , the dose should be increased to 180 mg for the remainder of the trial (see [Figure 2](#)).

For ongoing patients under the previous protocol amendment (Pre-Extended Dosing Period, see [Figure 3](#)), EV1 should be conducted at the following time points:

1. For ongoing patients with  $\geq$  12 weeks since the EOT visit: Conduct EV1 as soon as Possible.
2. For ongoing patients still undergoing treatment or with  $<$  12 weeks since the EOT visit: Conduct EV1 at the time of the next scheduled treatment or follow up visit (note: EV1 should not be conducted at the time point of Visit 2 under the previous protocol, patients with Visit 2 as their next scheduled visit should have their EV1 replacing their Visit 3 instead)

**Figure 2. Guideline for assessment of dose adjustment**

\* EV stands for extended visit

\*\* Week 0 is the first scheduled visit after amendment approval.

**Figure 3. Visit schedule Pre-Extended Dosing Period**

Trial periods	Treatment period							Follow Up period			
	1 	2	3	Interim Contact	4	5	EOT	FU 1	FU 2	FU 3	EOS visit
Day	1	42	84	126, 210, 294, etc...	168	252	336		EOT +168	EOT +252	EOT +336
Week	0	6	12	18,30, 42, etc...	24	36	48	EOT +12	EOT +24	EOT +36	EOT +48
Visit window (days)	+7	±7	±7	±7	±7	±7	±7	±7	±7	±7	±7

If there are any tolerability issues, as assessed by the investigator, the patient will be discontinued.

The plaque psoriasis will be evaluated by PASI score at each visit. The standard clinical endpoints of PASI 50, PASI 75, PASI 90 and PASI 100 will be assessed at each visit based on the baseline PASI from Study 1311.2.

The end of study is defined as the date the last subject completes the Extended End-of-study visit.

#### 4.3 Sample Size

The sample size is determined by the completion of Study 1311.2 and the consenting for the extension.

Eligible subjects from Study 1311.2 will be offered participation in this OLE study at their respective or referring sites. The check for subject eligibility will be based upon a successful completion of the Study 1311.2, signing the informed consent for this study, and the other inclusion and exclusion criteria.

#### 4.4 Interim Analysis

Data will be reviewed periodically during the study by an independent Data Monitoring Committee (DMC).

## **5.0 Analysis Populations**

### **5.1 Definition for Analysis Populations**

#### **Intent to Treat (ITT) Populations:**

The ITT Population is defined as all subjects who receive at least one dose of study drug in the study.

#### **Safety Population:**

Safety Population is the same as ITT Population for this study. This population will be used to provide a comprehensive summary of safety.

### **5.2 Variables Used for Stratification of Randomization**

For this open-label study, no randomization of subjects into different treatment groups or stratification of randomization is required.

## **6.0 Analysis Conventions**

Since this is a single arm open-label continuation study, no statistical test will be conducted. Summary statistics will be provided.

#### **Definition of Baseline**

1. Baseline is defined as the last non-missing value on or before the date of the first dose of study drug in Study 1311.2. The efficacy analyses will use these baseline values. These baseline values will be referred to as "BL" in this document.
2. RZB baseline is defined as the last non-missing value on or before the date of the first dose of risankizumab either in Study 1311.2 or this study. For vital sign assessments, only assessments prior to first dose time will be considered, since vital signs are to be assessed both pre- and post-dose in some visits. These values

will be referred to as BL\_RZB in this document. BL\_RZB will be used for safety analyses.

### **Definition of Final Observation (Applicable to Safety Analyses)**

Final observation in the entire study is defined as the last non-missing observation collected within 105 days after the last dose of risakizumab.

### **Definition of Rx Days (Days Relative to the Date of First Dose of Study Drug)**

Rx days are calculated for each time point relative to the date of first dose of risakizumab in this study. They are defined as the number of days between the day of the first dose of risakizumab and the specific time point. Rx days are negative values when the time point of interest is prior to the first risakizumab dose day. Rx days are positive values when the time point of interest is on or after the first risakizumab dose day. The day of the first dose of risakizumab is defined as Rx Day 1, while the day prior to the first risakizumab dose is defined as Rx Day –1 (there is no Rx Day 0).

### **Definition of Analysis Windows**

All time points and corresponding time windows are defined based on Rx Days.

For efficacy analyses, local tolerability, laboratory parameters, study drug injections, and vital sign variables, analysis windows are constructed using the following algorithm:

- Determine the nominal Rx day for each visit (e.g., Week 4 [4 weeks after Baseline visit] equals Rx Day 29).
- In order to include all post baseline data, the first post-baseline interval starts on the first day after the first dose of risakizumab (Rx Day 2).
- Determine the window around a specific nominal Rx day by adding or subtracting half of the interval between adjacent visits (e.g., days between Week 2 and Week 4 is 14). The threshold between adjacent visits is determined by splitting the interval evenly between the visits. If the resulting

split is between Rx days, then the threshold is determined as the midpoint between the adjacent visits. If the resulting split is on an Rx day, then the threshold is determined as being between that Rx day and the Rx day prior to it (e.g., the split between Week 2 and Week 4 would be between Rx Days 22 and 23).

- If more than one assessment is included in a time window the assessment closest to the nominal day will be used. If there are two observations equidistant to the nominal day, the one after the nominal day will be used in analyses. If more than one post baseline assessment is included on the same day, then the worst assessment on that day will be used in analyses, except those specified in Section 11.0.

The protocol specified visits and corresponding time windows used in the efficacy analyses, study drug injections, local tolerability, clinical laboratory tests, and vital sign variables, are presented in the following **Table 1**.

**Table 1. Visit Windows for Analysis of PASI, sPGA, Pain Vas, DLQI, Study Drug Injections, Local Tolerability Assessment, Clinical Laboratory Tests, and Vital Signs**

Window label	Target day	Interval
Entry of this study a	1	$\leq 1^b$
Week 12	85	[2, 127]
Week 24	169	[128, 211]
Week 36	253	[212, 295]
...	...	...
Week K	$K \times 7 + 1$	$[K \times 7 - 40, K \times 7 + 43]$

a. There is no local tolerability measurements at entry of this study (Extended Visit 1).

b. If time is collected in vital signs, restrict to records prior to the first dose of RZB.

Note: Rx Day calculated relative to first dose date of risakizumab in this study.

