5. VARIABLES AND THEIR ASSESSMENT

5.1 EFFICACY - PHARMACODYNAMICS

5.1.1 Endpoints of efficacy

5.1.1.1 Primary endpoint of efficacy

The primary efficacy endpoint is achievement of a $\geq 90\%$ reduction in PASI score from baseline (i.e., achieving PASI₉₀) at week 48 in the Extended dosing period. Baseline PASI for this study is defined as the baseline PASI for the 1311.2 study.

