5.1.1.2 Secondary endpoints of efficacy

The following secondary endpoints will all be evaluated at week 48 in the Extended dosing period:

- achievement of PASI₅₀
- achievement of PASI₇₅
- achievement of PASI₁₀₀
- achievement of sPGA of clear or almost clear

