7.3.1 Primary analyses

The achievement of PASI90 at week 48 in the Extended dosing period is the primary efficacy endpoint, which is a binary variable.

For primary safety, the overall incidence rates of AEs, drug related AEs, and SAEs will be calculated.

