## **10.2 Key Efficacy Variables**

The following key efficacy variables will be summarized at Week 48:

- Proportion of subjects achieving  $\geq 90\%$  reduction in Psoriasis Area and Severity Index (PASI) score (PASI 90)
- Proportion of subjects achieving the Static Physician Global Assessment (sPGA) score of clear or almost clear
- Proportion of subjects achieving  $\geq 50\%$  reduction in PASI score (PASI 50)
- Proportion of subjects achieving  $\geq 75\%$  reduction in PASI score (PASI 75)
- Proportion of subjects achieving 100% reduction in PASI score (PASI 100)
- Proportion of subjects achieving the sPGA score of clear

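### SAP efficacy Week 48 is counted from the first dose in this study, not from Extended Visit 1 as the protocol requires

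*SAP*

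**What the plan says.** Protocol 5.1.1.1 sets the primary efficacy endpoint, PASI90, "at week 48 in the Extended dosing period". Section 5.1.1.2 does the same for PASI50, PASI75, PASI100 and sPGA: "The following secondary endpoints will all be evaluated at week 48 in the Extended dosing period". Section 7.3.1 repeats it for the primary analysis: "The achievement of PASI90 at week 48 in the Extended dosing period is the primary efficacy endpoint". The Flow Chart for the Extended Dosing Period puts EV1 at Day 1, week 0, and EV5 at week 48.

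SAP 6.0 uses another origin. Under Definition of Rx Days: "Rx days are calculated for each time point relative to the date of first dose of risakizumab in this study". Under Definition of Analysis Windows: "All time points and corresponding time windows are defined based on Rx Days". The note to Table 1, whose title covers PASI, sPGA, Pain VAS and DLQI, repeats it: "Note: Rx Day calculated relative to first dose date of risakizumab in this study". SAP 10.2 then says only "The following key efficacy variables will be summarized at Week 48", without the words that tie week 48 to the Extended period.

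Both documents (Protocol 3.1 and 6.2.2.1, SAP 4.2) describe patients who were already in this trial on a Pre-Extended schedule and moved to EV1 later. EV1 may not take the place of old Visit 2 (week 6); such patients have EV1 at old Visit 3 (week 12). Patients at least 12 weeks past their old end-of-treatment visit have EV1 as soon as it can be arranged.

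**The concern.** For a patient already dosed in this study before EV1, Rx Day 1 is not EV1, and no SAP rule moves the origin. Programmed as written, the Week 48 efficacy summary would combine patients at Extended week 48 with patients at an earlier Extended week, and in some cases with patients who had not yet reached EV1.

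The timing matters because of the dose step. Under Protocol 3.1, patients below PASI90 at EV2 move from 90 mg to 180 mg, and Flow Chart footnote 21 requires efficacy to be assessed before dosing. A reading taken too early in the Extended period therefore reflects fewer 180 mg doses than the protocol's time point does, possibly none.

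The error would not show in the output. The Table 1 windows are contiguous, so a value from the wrong visit fills the Week 48 cell. SAP 10.1 uses observed cases, so the patient is counted as observed rather than missing.

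**Working it through.** **Inputs**
- SAP Table 1: Week K has target Rx day 7K + 1 and window [7K − 40, 7K + 43].
- Protocol Flow Chart: EV visits every 12 weeks; EV1 = week 0, EV5 = week 48; ±7 days.
- Protocol Figure 3.1:3 and SAP Figure 3: old Visits 2, 3, 4, 5 and EOT at weeks 6, 12, 24, 36 and 48; ±7 days, with +7 for Visit 1.
- Assumption: first in-study dose at old Visit 1. The current text has no dosing row for the old schedule. A later first dose shrinks the shift.

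**Reproducing Table 1.** K = 24 gives [128, 211] and K = 36 gives [212, 295], as printed. K = 48 gives target 337 and window [296, 379]. K = 60 gives [380, 463].

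**When EV5 falls in the SAP Week 48 window.** With L the days from first in-study dose to EV1, nominal EV5 is Rx day 1 + L + 336.
- L = 0: EV5 = 337, and the two origins agree.
- EV5 on its target day: 337 + L ≤ 379, so L ≤ 42 days.
- EV5 seven days early: 330 + L ≤ 379, so L ≤ 49 days.

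**Smallest lag for a patient dosed earlier in this study (EV1 at old Visit 3)**
- SAP day count, Visit 3 and EV5 both 7 days early: EV1 = 85 − 7 = 78; EV5 = 78 + 336 − 7 = 407, which is 28 days past 379.
- Protocol day labels (Day 84, Day 336): EV1 = 84 − 7 = 77; EV5 = 77 + 335 − 7 = 405, which is 26 days past.
- Old Visit 1 also 7 days late (Day 8) and Visit 3 on Day 77: EV1 = Rx day 70; EV5 = 70 + 335 − 7 = 398, which is 19 days past.

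All three fall in the Week 60 window.

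**What the SAP would read as Week 48 (nominal timing)**

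| EV1 takes the place of | EV1 Rx day | Visit on Rx day 337 | 180 mg doses possible before that reading | EV5 Rx day | SAP label for EV5 |
|---|---|---|---|---|---|
| none (first dose at EV1) | 1 | EV5 | 3 | 337 | Week 48 |
| old Visit 3 | 85 | EV4 (Extended week 36) | 2 | 421 | Week 60 |
| old Visit 4 | 169 | EV3 (Extended week 24) | 1 | 505 | Week 72 |
| old Visit 5 | 253 | EV2 (Extended week 12) | 0 | 589 | Week 84 |
| old EOT at week 48 | 337 | EV1, pre-dose | 0 | 673 | Week 96 |

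The dose counts follow from pre-dose assessment: by EV5 an escalated patient can have had 180 mg at EV2, EV3 and EV4.

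If EV1 comes 12 weeks after a week-48 EOT, it is on Rx day 421. The Week 48 window then closes 421 − 379 = 42 days before EV1, and a later EV1 widens the gap.

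**Effect on the proportion.** If a fraction f of observed patients is affected, the Week 48 PASI90 proportion shifts by f × (rate at the mistimed visit − rate at EV5). The documents give none of these three quantities, so neither size nor direction can be computed.

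**The case against.** The strongest reply is that EV1 was plainly intended. Table 1 lists entry and then Weeks 12, 24, 36 and onward, which matches the Extended Flow Chart and has no row for old Visit 2 at week 6. Footnote a identifies study entry with Extended Visit 1, and SAP 10.3 speaks of Extended dosing period visits. That reading of intent is reasonable, but it does not override a computational rule stated three times in the section that guides programming. Nor is the change declared: where the SAP departs from the protocol on laboratory grading (11.3.2), it says so and gives its reason.

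Second, the reach is unknown. The documents do not say how many patients were dosed in this study before EV1, or at which old visit that dosing began. This stands. It limits what can be said about impact, but not the finding that the two origins differ.

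Third, the consequences are modest: safety is the primary objective in Protocol 2.2, nothing is tested, and PASI and sPGA are summarised at every visit. This also stands and caps the severity. The every-visit tables are only a partial remedy, however. The displaced EV5 values sit under Weeks 60, 72, 84 or later, pooled with other patients' values, so the planned tables would not give back an Extended week 48 proportion.

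**Conclusion.** The concern holds and should be fixed. As written, the SAP does not analyse the protocol's primary efficacy time point for patients dosed in this study before EV1. On the assumption that in-study dosing began at old Visit 1, no such patient on schedule has EV5 inside the SAP Week 48 window: the closest case is Rx day 398 against an upper limit of 379. Nominally the Week 48 reading is 12, 24 or 36 weeks too early in the Extended period for EV1 at old Visit 3, 4 or 5. It is EV1 itself, or wholly before EV1, for those who moved over at or after a week-48 EOT.

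Patients whose first dose in this study is at EV1 are unaffected. The conflict between the texts is certain; the number of patients it touches is not known. The underlying data remain in the database, so the fault is one of labelling and pooling.

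**What to change.** In SAP 6.0, define Extended Day 1 as the date of the EV1 dose. Use it in place of Rx Day 1 for the Table 1 windows of PASI, sPGA, DLQI and Pain-VAS in SAP 10.2 and 10.3. The Week 48 window of 296 to 379 then contains EV5 at 337 ± 7 (330 to 344) for every patient on schedule. In 10.2, state that Week 48 means week 48 of the Extended dosing period.

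Keep efficacy data collected in this study before EV1 out of these summaries, and list or summarise them separately. It would help to report how many patients in the ITT population had no EV1 dose. Keep the first-dose origin for safety, as in the TEAE definition in SAP 11.2.1, and state in Table 1 which origin each variable uses.

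Do not take the Figure 2 note on Week 0 as the definition. For a patient whose next visit was old Visit 2, its wording puts Week 0 at Day 42 and EV1 at Day 84, a gap of 42 days, so it needs reconciling with the Visit 2 rule.

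The cost is SAP wording and one derived date before database lock, with no new data and no effect on patients. The one drawback is that Week 48 will have a different origin in the efficacy tables than in the laboratory, vital-sign, local-tolerability and injection tables, so each table must state its origin.

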### **Definition of Missing Data Imputation**

No global imputation is taking place at the database level. Efficacy related imputations are outlined in Section 10.0. There is no imputation for missing values in the safety analyses.

### **Rounding of Numeric Results**

Rounding will be performed for presentation of results. No rounding will be performed before or during analyses. The ROUND function of SAS will be used to round results.

When dichotomizing continuous variables, associated continuous variables will be rounded to 9 decimal points before applying the cutoff point to determine the response status (for example, percent change from baseline in PASI score will be rounded to 9 decimal places before comparing to 90%).

The mean and median will be rounded for presentation to 1 decimal more than the data entered into the database. The standard deviation will be rounded to 2 decimal places more than the data entered into the database. The minimum and maximum values will be presented as entered into the database.

Probabilities will be rounded to 3 decimal places before assignment of statistical significance and will be presented in rounded format. Probabilities that round to zero or are reported by SAS as zero will be presented as "< 0.001." Probabilities that round to 1 or are reported by SAS as 1 will be presented as "> 0.999."

## **7.0 Demographics, Baseline Characteristics, Medical History, and Previous/Concomitant Medications**

### **7.1 Demographic and Baseline Characteristics**

Demographics and Baseline characteristics will be summarized for ITT population. Continuous variables will be summarized with the number of non-missing observations by mean, standard deviation, median, minimum and maximum values. Categorical data

will be summarized using frequencies and percentages. No Statistical tests will be performed for this study.

The following demographic and baseline parameters will be summarized.

### **Subject Demographics**

- Sex (male, female)
- Age (years), defined as the number of years from date of birth to date of first drug
- Age categories (< 40 years,  $\geq$  40 – < 65 years,  $\geq$  65 years.)
- Race (American Indian or Alaska Native, Asian, Black or African American, Native Hawaiian or Other Pacific Islander, White, Multiple)
- Ethnicity (Hispanic or Latino, Not Hispanic or Latino)
- Body weight (kg)
- Body weight category ( $\leq$  100 kg,  $>$  100 kg)
- Height (cm)
- BMI ( $\text{kg}/\text{m}^2$ )
- BMI category (< 25,  $\geq$  25 – < 30,  $\geq$  30)
- Prior exposure to TNF antagonists (0 versus  $\geq$  1)

### **General Baseline Characteristics**

- PASI (Psoriasis Area and Severity Index)
- BSA (Body Surface Area)
- sPGA (Static Physician Global Assessment)
- NAPSI (Nail Psoriasis Severity Index)
- PSSI (Psoriasis Scalp Severity Index)
- PPASI (Palmoplantar Psoriasis Area Severity Index)
- Dermatology Life Quality Index (DLQI)

## **Psoriasis and Cardiovascular History**

- Psoriatic arthritis (diagnosed, suspected, no)
- Cardiovascular Diseases (angina pectoris, atherosclerosis, cerebrovascular accident, congestive heart failure, coronary artery disease, myocardial infarction, peripheral arterial disease, stroke, transient ischemic attack)
- Cardiovascular Risk Factors (hypertension, hyperlipidemia, diabetes mellitus (includes both type 1 and type 2))

## **General Use**

- Smoking status (Never-smoked, Ex-smoker, Currently smokes)
- Alcohol status (Non-drinker, drinks – no interference, drinks – possible interference)

Also, Physical Exam and Pregnancy Test will be presented in listing format.

## **7.2 Medical History**

Medical history (at the time of enrollment in the Study 1311.2) will be summarized using body systems and condition/diagnosis as captured on the eCRF. The body systems will be presented in alphabetical order and the conditions/diagnoses will be presented in alphabetical order within each body system. The number and percentage of subjects with a particular condition/diagnosis will be summarized for each treatment arm. Subjects reporting more than one condition/diagnosis within a body system will be counted only once for that body system.

